5. SAMPLE SELECTION

Cases. Patients with PAF who present to Electrophysiology (EP) Clinic at UHCMC and the Cleveland Clinic Foundation (CCF) will be approached for recruitment in the study.

Inclusion Criteria for Cases: 1) *PAF defined by recurrent episodes of AF, which self-terminate within a 7-day period (based upon AHA consensus statement 77)*, 2) Age 18-80 years, 3) Individuals able to participate in ≥ 2 overnight/daytime sleep and physiologic assessments over a 3 month period.

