
Elucidation of the Influence of Sleep Apnea on Risk of Atrial Fibrillation PI- [name] and [name]

arrhythmogenesis. Those with unstable medical conditions or rapid or uncontrolled heart rate will be excluded due to safety reasons.

Note: Exclusion criteria for positive airway pressure (PAP) intervention: Central Apnea Index \geq 5 noted on baseline examination sleep study or evidence of Cheyne Stokes Respirations/periodic breathing (cyclical crescendo and decrescendo change in breathing amplitude).

We plan to recruit 10 cases with moderate to severe SDB and paroxysmal AF who are placed on CPAP to participate in an ancillary study to investigate the effect of CPAP on the default mode network, which is a well-established resting state network in the brain that is involved in semantic processing and associated with compromise in cognitive task performance.

Note: Exclusion criteria for the 7T MRI would include ferrous objects in the body (cochlear (ear) implant, brain aneurysm clip, stimulator device, and cardiac pacemaker), severe kidney disease, and history of claustrophobia.

Controls. Patients without AF will be recruited from the UHCMC and CCF General Cardiology and Internal Medicine clinics (geographically similar to controls). Selection bias will be minimized as there are a broad range of reasons for patients to present to these clinics.

Inclusion Criteria for Controls: 1) Age 18 to 80 years, 2) Individuals in normal sinus rhythm (NSR) with no current AF or history of AF 3) Individuals able to participate in an overnight/daytime sleep and physiologic assessment.

Exclusion Criteria for Controls: Current or history of AF, otherwise the same exclusion criteria listed for cases.

We plan to recruit 10 controls without PAF but with moderate to severe SDB to participate in an ancillary study to investigate the default mode network, which is a well-established resting state network in the brain that is involved in semantic processing and associated with compromise in cognitive task performance. The controls will have the cognitive battery and questionnaires only. They will not undergo the 7T MRI.

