MATCHING. Cases and controls will be individually matched to enhance study efficiency and precision with more stable odds ratio estimates and narrower confidence intervals. Matching will be based upon factors which are biologically strong confounders as follows: 1) age (\pm 5 years), 2) gender, 3) race (*white* versus *non-white*) and 4) obesity (BMI $+\text{-}2$ kg/m^2). Recruitment of controls and cases will be contemporaneous given concurrent assessments of eligibility (AF status and matching criteria). To ensure appropriate individual matching on the factors listed above, a staggered recruitment of controls will occur such that matching parameters will change monthly depending upon the distribution of these factors in the case group. Statistical code will be written to perform matching of cases and controls with these five

Elucidation of the Influence of Sleep Apnea on Risk of Atrial Fibrillation PI- [name] and [name]

variables. If exact control matches are not identified, then unmatched cases will be retained in the cue until the next round of matching.

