8. STUDY PROCEDURES AND DATA COLLECTION

2-DIMENSIONAL DOPPLER ECHOCARDIOGRAPHY. **Procedure:** Participants will be studied by one of two senior sonographers during quiet respiration in the left lateral decubitus position with administration of intravenous agitated saline to enhance imaging. Parasternal, apical and subcostal 2-D views and apical 3D views will be obtained with transducer orientation and gain settings adjusted to optimally define endocardial surface of each cardiac chamber. Measurements will be performed by the Director of the ECHO Lab (accredited by the Intersocietal Commission for the Accreditation of Echocardiography Laboratories), [name] (Co-I) and designate off-line (HeartLabs Inc, Q Labs, Phillips Medical) in a blinded fashion on 3 representative beats and the results averaged. Measurements will be performed according to the American Society of Echocardiography recommendations ^{79,80}. Studies will be archived on CD. Rigorous quality control measures will be used including random repeat measurements to calculate inter- and intra-observer reliability.

Approximately 20% of echocardiograms result in suboptimal views in at least 2 of 6 myocardial segments of the left ventricle in apical views. The use of a contrast agent can opacify the sub optimally viewed areas allowing for better analysis. Individuals with obesity, lung disease, or other critical care areas usually require the use of a contrast agent for optimal echocardiogram views. Subjects requiring a contrast dye will be administered an IV dose of Definity ® (perflutren lipid microsphere injectable suspension), a US Food and Drug Administration (FDA) approved contrast dye. Subjects will be screened for known contraindications: known or suspected cardiac shunts or patent foramen ovale, or known hypersensitivity to perflutren. Subjects will also be informed of the potential risks

associated with Definity ® as described in the informed consent document.

Relevant ECHO Variables:

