10. DATA ANALYSIS

EXPOSURES: *Primary:* 1) SDB defined by AHI, i.e. number of apneas + hypopneas/hour of sleep. *Secondary:* 1) Hypoxia: % sleep time with $\text{SaO}_2 < 90\%$, 2) Obstructive Sleep Apnea [obstructive apneas and hypopneas/hour of sleep, obstructive apnea hypopnea index (OAHI)], 3) Central Sleep Apnea [central apneas/hour of sleep, Central Apnea Index (CAI)], 4) Periodic Breathing and 5) EEG arousals [per hour of sleep, Arousal Index (AI)].

OUTCOME: 1) PAF (SA1) and 2) AF burden defined as frequency of AF paroxysms overall and based on self-reported sleep vs. wake (SA2 and 3)

COVARIATES: Age, race, body mass index (BMI, kg/m^2), waist circumference (cm), anti-arrhythmic/beta blocker/calcium channel blocker/ACE inhibitor/angiotensin receptor blocker medications, pacemaker, defibrillator, heart failure (NYHA class), BP, diabetes mellitus, left atrial volume, LVEF, caffeine use, alcohol use and smoking (current versus never smoker or pack years) and activity level. When assessing hypoxia as the relevant exposure, pulmonary disorders will be included as potential confounders.

Table 2. Mediator (SA1) or Outcome (SA3)

Domain	Primary	Secondary	Rationale
Echocardiographic Measures	Left Atrial Volume (ml/m^2)	LA Pressure, LA Systolic Strain, RA area, RA Pressure, LAA Peak Anterograde Flow Velocity (cm/s), Right Atrial Pressure (mmHg), LVEF, LVMI, LVH (concentric LVMI >0.41 , eccentric ≤ 0.41).	Left Atrial Volume predicts risk of AF and PAF ¹⁰³⁻¹⁰⁶ . Secondary measures also associated with AF.
Autonomic Function (Heart Rate Variability)	SDNN (ms) (Time Domain HRV Measure)	Time Domain (r-MSSD (ms), pNN50), Frequency Domain [LF (Hz), HF (Hz), LF/HF], Graphical Parameters (HR patterns, power spectral analysis, Poincaré plots and beat-by-beat HR tachograms) and Novel non-linear measures (e.g. Conditional Entropy ¹⁰⁷).	Reduced SDNN and LF/HF have been identified as AF triggers ⁴⁰ .
Systemic Inflammation	hs-CRP (mg/L)	IL-6 (pg/ml), sIL-6R (ng/mL)	hs-CRP and IL-6 associated with SDB and AF ⁴⁷⁻⁴⁹ . s-IL6R varies with overnight hypoxia ⁴⁶
Oxidative Stress	Endothelin-1 (pg/ml)	Urinary isoprostane 8-epi-prostaglandin F2a (ng/ mmolCr), Oxidized LDL (U/L)	Endothelin-1 implicated in AF ⁵⁷⁻⁵⁹ . Isoprostane ⁶⁰⁻⁶² and oxidized LDL sensitive to SDB ⁷⁶ .

ANALYTIC METHOD BY AIM.

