Although the clinics will be the primary source of recruitment, controls we will also assess eligibility of individuals from the UHCMC/CCF Echocardiography Database (>10000 ECHOs/year). [name] will identify patients who meet matching criteria (left ventricular function, age, sex, race) based upon the cases who have been enrolled in the study. Referring physicians will be notified through emails or phone calls when eligible patients are identified. A letter signed by [name], the PI and the physician who referred the patient for the ECHO will then be sent to these patients describing the research study and providing study contact information. A time will be arranged for the patient to meet the research staff in a face to face meeting fully review the protocol and obtain informed consent.

B. PROTECTION AGAINST RISKS

All participant information will be kept strictly confidential and used for research purposes only. Records will be identified by a subject ID number rather than the subjects' name, and all will be secured in locked files in secured rooms. Computers are located in restricted access research suites; computer information is protected by use of passwords and a firewall. Computer files do not permit linking individual data with medical or other data collected for research purposes. The list of names and identification numbers will be stored separately from other data in locked files to which project staff only will have access. Informed consents explicitly state that information on non-paternity is never revealed. All presentations and publications will only utilize aggregate data.

Data transmission between the Electrophysiology Core and Echocardiography Laboratory and the Administrative Center-CC will be accomplished through a secure, password protected website using a Virtual Private Network (VPN), an established method for secure transfer. Implementation of this method will prevent unauthorized viewing of participant information during data transmission. The Administrative Center-CC and Cores will not receive any information allowing participant identification. Participant data received by the Administrative Center-CC will be identified only by the participant ID.

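### SA1 draws cases and controls from two hospitals but neither matches on nor adjusts for site, so pairs can span hospitals and a site difference in AHI can bias the odds ratio

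*Combined protocol and SAP*

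**What the plan says.** **Recruitment (Section 5).** For cases, patients presenting to the "Electrophysiology (EP) Clinic at UHCMC and the Cleveland Clinic Foundation (CCF) will be approached for recruitment". For controls, "Patients without AF will be recruited from the UHCMC and CCF General Cardiology and Internal Medicine clinics". Section 11 adds the two hospitals' echocardiography database as a further source of controls. Overnight visits take place in two research units (Sections 2 and 7).

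**Matching (Section 5).** "Matching will be based upon factors which are biologically strong confounders as follows": age, gender, race and BMI. The same paragraph then says "Statistical code will be written to perform matching of cases and controls with these five" variables, although it has named four. For echo-database controls, Section 11 gives "matching criteria (left ventricular function, age, sex, race", which includes left ventricular function and omits BMI. Neither list contains site.

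**Analysis (Sections 9 and 10).** SA1 is a conditional logistic regression on the matched pair. The covariate list is clinical and behavioural and ends with "caffeine use, alcohol use and smoking (current versus never smoker or pack years) and activity level", plus pulmonary disorders when hypoxia is the exposure. No SA1, SA2 or SA3 model has a site or operator term.

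**Echo (Section 8).** "Participants will be studied by one of two senior sonographers". Measurement is off-line and blinded. No rule keeps the same sonographer for a participant's two SA3 visits.

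**The concern.** Conditional logistic regression removes only what the two members of a pair share. If a case from one hospital is paired with a control from the other, they do not share site. Cases come through electrophysiology clinics and controls through general clinics and an echo database, so the two groups' site shares need not agree, and nothing in the plan holds them together. If the hospitals also differ in AHI after matching, through patient mix or through how the sleep study is acquired, part of the SA1 odds ratio is a hospital effect. SA1 is the aim that carries the study's main association, so this is where the omission matters.

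**Working it through.** **The plan's own figure.** SA1 states that 300 subjects detect an odds ratio of 1.50 per SD of AHI with 80% power (1.60 with 90%), two-sided alpha 0.05, probability of PAF 0.20, zero correlation. Using n = (z for alpha/2 + z for power)² / [P(1 − P)(ln OR)²]:

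- OR 1.50, 80%: (1.960 + 0.842)² / [0.16 × (0.4055)²] = 298.4
- OR 1.60, 90%: (1.960 + 1.282)² / [0.16 × (0.4700)²] = 297.3

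Both agree with 300. The calculation makes no allowance for site.

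**Inputs for the site check.** From the documents: 150 pairs, zero within-pair correlation, conditional logistic model. Assumed, because the documents give no figures: the two hospitals' shares of cases and of controls, and the difference in AHI between hospitals that remains after matching (0.2 to 0.5 SD).

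**Size of the bias with no true effect.** If pairing ignores site, the case-control difference in mean AHI is (site share in cases − site share in controls) × offset. For a normally distributed exposure scaled to unit SD, this is approximately the log odds ratio per SD. The last two columns come from simulating the pair-conditioned model without a site term.

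| Site mix, cases vs controls | Offset (SD) | Closed form | Simulated OR per SD | Type I error |
|---|---|---|---|---|
| 50/50 vs 50/50 | 0.2 to 0.5 | exp(0) = 1.00 | 0.998 | 0.046 to 0.050 |
| 60/40 vs 40/60 | 0.2 | exp(0.04) = 1.041 | 1.038 | 0.060 |
| 60/40 vs 40/60 | 0.3 | exp(0.06) = 1.062 | 1.059 | 0.073 |
| 60/40 vs 40/60 | 0.5 | exp(0.10) = 1.105 | 1.104 | 0.126 |
| 70/30 vs 30/70 | 0.2 | exp(0.08) = 1.083 | 1.084 | 0.091 |
| 70/30 vs 30/70 | 0.3 | exp(0.12) = 1.127 | 1.130 | 0.168 |
| 70/30 vs 30/70 | 0.5 | exp(0.20) = 1.221 | 1.212 | 0.376 |

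With site in the model, type I error is 0.04 to 0.05 throughout.

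**With a true odds ratio of 1.50 and an offset of 0.3 SD.** The unadjusted estimate is 1.59 at 60/40 (1.50 × exp(0.06) = 1.59) and 1.70 at 70/30 (1.50 × exp(0.12) = 1.69). With site as a covariate it is 1.51 to 1.52.

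**Cost of adjusting.** Simulated power at 1.50 is about 0.93 with site-matched pairs. With site as a covariate it is 0.91 at 60/40 and 0.83 at 70/30. The loss arises because cross-site pairs then run mostly one way: at 70/30, 0.7 × 0.7 = 49% of pairs have the case at the first hospital and the control at the second, against 0.3 × 0.3 = 9% the other way. The simulation starts above 80% because half its subjects are cases; with P = 0.50 the formula above gives 191, not 298.

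**SA3 echo.** A sonographer who is the same at both visits cancels in the paired difference. If the sonographer is random at each visit, the operator term in the difference is −1, 0 or +1 with probabilities 1/4, 1/2, 1/4, so its variance is 1/2. For an operator offset of 0.3 SD of the paired difference, the SD rises by the factor √(1 + 0.5 × 0.3²) = 1.022, or 2.2%, with no bias and type I error 0.05.

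**The case against.** Several points on the other side have force.

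- **The size is hypothetical.** Bias needs both unequal site mix and unequal AHI after matching on age, gender, race and BMI; the adjusted models add waist circumference and more. Both groups come from the same two hospitals over the same period. This stands, and is why the sizes are given as an assumed range that includes nil. A reader might infer from more extreme splits that site alone could produce an odds ratio as large as those SA1 is powered for. The documents do not support that.
- **Sleep-study measurement is protected.** There is one named PSG system, calibration by a certified technician, documented scoring criteria, and blinded certified scorers. This reduces measurement differences between hospitals. It does nothing about differences in the patients.
- **Site might be the fifth matching variable, or be handled elsewhere.** The text does not name the fifth. Section 11 points towards left ventricular function, without settling it. The text under the last subheading of Section 6, on recruitment sites, was not available for this review, so a site rule there cannot be ruled out.
- **The two remedies pull against each other.** Same-site pairs carry no information on a site coefficient, so preferring them weakens the site term. This is correct and shapes the fix.

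A reader might also infer from the two-sonographer arrangement that operator differences could pass for a CPAP effect in SA3. The documents do not support this. The SA3 primary outcome is AF paroxysm frequency from ambulatory ECG, which no sonographer touches, and SA3 is described as not confirmatory. Random switching adds slight noise. Only a one-directional change of operator between visits would bias the echo change, and nothing in the plan suggests one.

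**Conclusion.** The point holds for SA1. As the plan reads, pairs may span hospitals, neither pairing nor model controls site, and a hospital difference can bias the odds ratio in either direction. Under the assumed offsets of 0.2 to 0.5 SD, the false odds ratio is 1.04 to 1.10 per SD for a 60/40 versus 40/60 mix and 1.08 to 1.21 for 70/30 versus 30/70. With equal site mix it is 1.00. These figures rest on assumed site shares, an assumed residual AHI difference, normally distributed AHI and zero within-pair correlation. The lower end is small against the stated detectable 1.50; at the upper end type I error reaches 0.38. This is a gap to close cheaply, not evidence that SA1 is biased. The sonographer matter is secondary and concerns only the precision of SA3 echo outcomes such as left atrial volume.

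**What to change.** 1. **Matching code:** in each monthly round, take a same-site control first when more than one is eligible.
2. **Section 5:** name the fifth matching variable, and reconcile the list with the echo-database criteria in Section 11.
3. **SA1 models:** add site as a binary covariate to the conditional logistic models while cross-site pairs remain, and report cases, controls and cross-site pairs by hospital. If nearly all pairs are same-site, the pairing already controls site and the term can be omitted. If the remaining cross-site pairs all run in one direction, the site coefficient cannot be estimated and those pairs add nothing once site is in the model; the estimate then rests on same-site pairs, and the report should say so.
4. **SA3 echo:** record sonographer ID and book the baseline sonographer for follow-up where possible.

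The cost is a tie-break in the code, some SAP wording, one parameter and slightly tighter echo scheduling. Precision falls when site mix is unbalanced: simulated power at 1.50 is 0.91 at 60/40 and 0.83 at 70/30, against about 0.93 with site-matched pairs, still above the stated 80%. Those powers assume pairing that ignores site; the tie-break itself was not simulated. No larger sample is implied by these figures.

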6. RECRUITMENT OVERVIEW

The site's study Research Coordinator will oversee recruitment efforts. Patients with PAF who present to Electrophysiology (EP) Clinic at UHCMC and CCF will be approached for recruitment in the study. [name], Director of CCF EP Program and [name] (Co-I), Director of the UHCMC EP Center and 6 other electrophysiologists including [name] (Director of Electrophysiology Research, Co-I) comprise the EP clinical team along with the EP fellowship program/clinic. Approximately 1,680 new patients/year (140/month) with AF are seen in the EP clinics. Of these, ~672 patients/year (~60/month) have PAF. Assuming 50% meet eligibility criteria and 50% of those are interested then ~n=168 patients will be recruited/year (n=14/month). This translates into n=672 potential participants over the 4 year recruitment period which far exceeds the n=150 cases required to meet sample size requirements. As part of clinical care, PAF patients have echocardiograms, may be treated with ablation or anti-arrhythmic medications and often will undergo Holter ECG monitoring. Only those patients with PAF diagnosed within the last 6 months who have not undergone ablation will be approached for enrollment.

A screening form will be designed to identify eligibility criteria. Once a person has been identified as eligible to participate in the study, written informed consent and HIPAA authorization will be obtained. To maintain general descriptive information about the target sample, the screening questionnaires will be entered into a secure research database that does not include any personal identification. All hard copies of this health information will be destroyed about all patients who do not meet study criteria and those who decline participation. All personal health information collected and retained on site prior to obtaining written authorization will be de-linked from identifying personal information. Also, if written authorization is not obtained within 90 days of patients who have agreed to participate in the study, their health information will be destroyed.

Recruitment Sites and Sources

This is a request for partial waiver of HIPAA authorization" to collect health information" from screening questionnaires or from the medical records of participating electrophysiology clinics. The screening questionnaires will ask health questions to screen for sleeping patterns, and personal health information to determine which patients would qualify for study participation. The medical record screening form identifies eligibility criteria. Once a person has been identified as eligible to participate in the study, they will be scheduled for an in-person study visit at which time, written informed consent and HIPAA authorization will be obtained. (If the patient is available at the time of the screening, as may occur if the screening questionnaire is directly administered, the full screening visit may be conducted at that time in an area sufficiently private to provide for confidentiality. To maintain general descriptive information about the target sample, the screening questionnaires will be entered into a secure research database that does not include any personal identification. All hard copies of this health information will be destroyed about all patients who do not meet study criteria and those who decline participation. All personal health information collected and retained on site prior to obtaining written authorization will be de-linked from identifying personal information. Also, if written authorization is not obtained within 90 days of patients who have agreed to participate in the study, their health information will be destroyed.

13. Electronic Record System Utilization

Eligibility will be assessed by a study recruiters ([name] (UH) and [name] (CCF)) and the study coordinator ([name] (CCF)) using the UH and CCF Physician Portal. This will be done by accessing each potentially eligible patient's electronic chart only once in order to review the most recent note from the patient's cardiologist. Information viewed will be used by the study recruiter to check yes or no on the study inclusion and exclusion criteria form with no recording of specific results being made. These forms are de-identified with only the study id listed. No printouts from the Portal will be made. Review of the chart should take no more than 5 minutes per patient. All hard copies of this health information will be destroyed about all patients

who do not meet study criteria and those who decline participation. All personal health information collected and retained on site prior to obtaining written authorization will be de-linked from identifying personal information. Also, if written authorization is not obtained within 90 days of patients who have agreed to participate in the study, their health information will be destroyed.

The reason for requesting access to physician notes on the Portal rather than reviewing paper charts is that paper charts are not stored at each clinic but are instead stored at an off site locality where they are not accessible for review until 24 hours prior to the patient appointment. Because the recruiter is expected to be at a clinic each day, he cannot physically review paper charts until the day of clinic but this is disruptive to patient care. By utilizing the UH Portal, the recruiter can screen for eligible patients without interfering with clinical care.

If questions arise relevant to eligibility (e.g., degree of renal insufficiency, time since free of cancer) that cannot be readily answered by the recruiter, one of the study physicians (at UHCMC, Drs. [name], [name], [name] and [name] and at the Cleveland Clinic, Drs. [name] and [name]) who already has Portal access will use the Physician Portal to access the relevant clinical notes or laboratory information to make a judgment on study eligibility. It should be noted that this study physician may not be a direct caregiver of the patient. The recruiter will get approval from the patient's physician prior to accessing the patient's record for screening. Access to electronic records will be made at most once per patient by a study physician to determine eligibility and only in those cases where staff has been unable to make a clear determination through review records in the clinic and interview with the patient. We anticipate this will be required in less than 5% of screenings. Information viewed will be used by the study physician to check yes or no on the inclusion and exclusion criteria with no recording of specific results being made. These forms are de-identified with only study id listed. No printouts from the Portal will be made.

Similarly, in dealing with potential safety concerns, one of the study physicians at UHCMC, Drs. [name], [name], [name], and [name] and at the Cleveland Clinic, Drs. [name] and [name]) may access the Physician Portal to stratify adverse events. For example, if overnight cardiac monitoring reveals bouts of atrial fibrillation, identifying that the patient has a history of atrial fibrillation will make this finding a low level adverse event requiring only a letter to the patient's study physician. However, if review of the Physician Portal demonstrates the patient has no prior history of atrial fibrillation, this would result in a higher level adverse event where the patient's physician would be contacted within 24 hours to be notified of this important new finding. Again, the Portal would be accessed at most once per adverse event and only if it was unclear if the finding were new (e.g., there would be no need if the patient reported he had a history of atrial fibrillation). This information will be recorded only in terms of grading adverse events, all of which again are on de-identified forms labeled only with a study id and no printouts of Portal information will be made. Using the Portal is necessary to obtain information relevant to patient safety in a timely manner as requesting paper patient outpatient charts can take up to a week.

